as well as racial and ethnic minorities if the study sample is skewed from the local patient demographic (i.e., ≤10% female; ≤ 16% racial/ethnic minority). Using previously effective recruitment methodology, candidates will be mailed introductory letters that describe the study (including an informed consent summary), how to volunteer, and how to opt out. Veterans who do not opt out will be considered eligible for recruitment phone calls. A trained RA will conduct recruitment phone calls to verify Veterans' age and contact information; establish capability of communicating in English; and provide additional information about the study. Interested candidates will then be offered time(s) to attend a remote (i.e., phone, telehealth) meeting to complete verbal informed consent procedures, that will include review of a detailed written summary of study procedures, and a screening/ baseline (T1) assessment. Candidates will have a copy of the consent summary in-hand as they review materials with staff. Eligible candidates will then be randomized 1:1 to the test or control condition. Follow-up contact (e.g., phone, mail, encrypted Azure email, video telehealth appointment) will take place on an as-needed basis, for instance, to schedule/ re-schedule study visits, respond to participant questions, clarify the nature missing or ambiguous responses on study measures, deliver telehealth/telephone sessions, distribute relevant handouts/ workbook materials, conduct participant outreach. Participants will have an option to directly enter patient-reported outcome data in the VA Qualtrics platform. A secure link to the data entry portal will be shared using secure communication methods outlined above. These multiple avenues for participant engagement are necessary as phase 2 study procedures will be conducted remotely.

Phase 2 Inclusion Criteria:

a) OEF/OIF/OND Veteran; b) ≥ age 18; c) enrolled in VA primary care (appointment within last 12 months); d) history of mTBI (as measured by the *Ohio State Traumatic Brain Injury Identification Method-Short Form*; OSU TBI-ID; Corrigan & Bogner, 2007); e) persistent post-concussion-like symptoms (as measured by the NSI; Cicerone & Kalmar, 1995); f) BSI-18 (Derogatis, 2001) GSI T-score > 53; g) English speaking, able to read and write, and able to comprehend study materials.

Phase 2 Exclusion Criteria:

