- **Demographic Survey:** The demographic survey will collect basic information on participants such as age, racial and ethnic background, gender, vocational, and socioeconomic status. Additional questions will inventory any PST-related and/or compensatory skills that Veterans may independently endorse prior to beginning study interventions.
- **OSU TBI-ID** (Corrigan & Bogner, 2007): A brief, structured screen designed to determine lifetime history of TBI by identifying possible head/neck injuries and associated loss or alterations of consciousness. Scores of 2 or 3 indicate a likely history of mTBI and will be used to establish inclusion criterion **d**. The OSU TBI-ID is a NINDS CDE.
- **Neurobehavioral Symptom Inventory (NSI;** Cicerone & Kalmar, 1995): A 22-item checklist of common affective, cognitive, and somatosensory symptoms commonly reported after concussion. Sample items pertain to dizziness, headaches, and forgetfulness. This measure is commonly used in VA's second-level TBI evaluations and is a NINDS CDE. An embedded Validity-10 index (Vanderploeg et al., 2014) estimates the likelihood of symptom exaggeration. Scores of 2 (moderate) or higher on at least one cognitive, affective, and somatic symptom will indicate possible persistent post-concussion-like symptoms (inclusion criterion **e**). Changes of ≥ 8 points indicate clinically-significant change (Belanger et al., 2016).
- **BSI-18** (Derogatis, 2001): The BSI-18 is a brief measure of psychological distress brought about by common somatic and affective symptoms. It has been validated for use in patients with history of TBI (Meachen et al., 2008) and is appropriate for use in primary care (Lang, 2005). BSI-18 GSI T-scores will be used to gauge inclusion criterion **f** and will serve as the primary outcome measure. A score > 0 on Item 17 will serve as a signal to conduct further suicide risk assessment per the attached protocol.
- **PHQ-9** (Kroenke et al., 2001): A standard measure of depression symptoms validated for use in primary care. This item is included in VA's Mental Health Assistant and is a supplemental NINDS common data element. A score > 0 on Item 9 will serve as a signal to conduct further suicide risk assessment per the attached protocol.

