Phase 2 Procedures.

Chart Pre-Screening. Study staff will review VISN2 primary care clinic lists for Veterans who have mTBI-related diagnoses listed in their EMR data (e.g., problem lists, corresponding ICD-9 or ICD-10 diagnostic codes); meet the age, service-era, and primary care enrollment criteria; and whose EMRs do not include any obvious evidence of exclusion criteria listed above. Recruitment letters and informed consent summaries will then be sent to veterans who pass the pre-screening procedure.

Recruitment Phone Calls. Veterans who pass pre-screening procedures and who do not opt-out will be contacted by phone to discuss the study and gauge interest. Interested candidates will then be scheduled for a verbal consent appointment and baseline assessment.

Screening/ Baseline Assessment & Selection. The written informed consent summary will be reviewed with candidates. Candidates will have a copy of the consent summary in-hand as they review materials with staff. Veterans who provide verbal consent will be formally screened for eligibility using the T1 measures outlined above.

Randomization. Following completion of the T1 assessment, eligible participants will be randomized in equal proportions to the test (E-PST) or control using a stratified permuted block design. Block designs ensure treatment balance of participants by randomly assigning the same number of participants to each treatment condition within blocks (e.g. ABBA, ABAB, etc.). A stratified design ensures treatment balance across 1 or more prognostic factors. We plan to implement a stratified permuted block design using blocks of size 4 within low and high levels of the baseline psychological distress as measured by the BSI-18: 1) “mild to moderate” (BSI-18 GSI T-score 54-62); and 2) “severe” (BSI-18 GSI T-score ≥ 63). Our block design maintains treatment balance within levels of baseline psychological distress while ensuring that the overall imbalance is not too great. Since we expect that an overall small number of female participants will be enrolled in the RCT, the treatment groups might be imbalanced by gender (i.e., because randomization is more effective with larger n ’s). To account for this possible gender imbalance, we will also equalize the treatment groups according to gender, which will minimize the chance of gender confounding the treatment effect.

Table 2. Phase 2 Assessment Schedule

Measure	Chart Pre-Screen	T1	Mid- Intervention	T2	T3
Chart Pre-Screening Tool	•				

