Primary analyses will focus on detecting post-treatment change in psychological distress as measured by the BSI-18's GSI T-score. We will test the preliminary hypothesis that E-PST (vs. control) will be associated with reduced psychological distress as measured by BSI-18. BSI-18 data will be described with means, standard deviations and CIs at each time point and condition. To show central tendency, variation and potential trends over time, means and 95% CIs will be plotted across time for each condition. Additional line plots connecting means across time will overlay the CIs to help illustrate trends. To assist in developing a larger trial, an ES will be calculated at post treatment to describe the standardized difference between conditions. The ES will be calculated by dividing the difference in the mean BSI-18 score between conditions at post-treatment by the pooled standard deviation. Then, the upper limit of a one-sided 80% CI under the null hypothesis of no difference between groups (ES = 0) will be compared to the observed ES by using the non-central *t*-distribution method discussed by Cumming & Finch (2001). We opted for a one-sided CI because we are interested in progressing toward a larger trial based on some evidence of effectiveness. The lower end of the CI is not informative in this pilot as the progression towards a larger trial would not occur even if the control condition was marginally more effective than E-PST. While a standard 95% CI provides greater coverage of the population difference, it also requires a larger sample of patients and associated increases in cost and time. Therefore, we propose an 80% interval that provides reasonable assurance of making the correct decision to move on to a larger trial (Cocks & Torgerson, 2013) While primary analyses focus on psychological distress, post-treatment ES's will also be calculated for secondary outcomes, and a correlation matrix will be built to describe the degree of correspondence among all outcomes. Our goal is to calculate a preliminary ES estimate that is representative of the true population using the ITT principle. Thus, all patients who are complete a baseline assessment and are randomized will be included in our analysis. We plan to utilize two sophisticated methods with the first being Maximum Likelihood Estimation (MLE), and Multiple Imputation (MI) as the second. A multi-level model (MLM) will be developed using MLE to calculate means and standard errors that will be used in the formation of an ES. MLM provides unbiased parameter estimates under a missing at random (MAR) assumption without resorting to listwise deletion of patients due to missing data. While the validity of MAR cannot be fully determined from the data, the reason for the missingness may depend on observed co-variates. If the latter case is true, MI (see below) is a viable and powerful option for imputing

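### The primary effect size ignores the T1 BSI-18 score; adjusting for it costs one degree of freedom and gives better precision and a better-calibrated 80% limit, by an amount that depends on an unstated correlation

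*Combined protocol and SAP*

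**What the plan says.** Phase 2 Data Analysis, a) Quantitative Data Analysis, gives one explicit formula for the ES: "dividing the difference in the mean BSI-18 score between conditions at post-treatment by the pooled standard deviation". It has no T1 term. The same section says a multi-level model (MLM) fitted by maximum likelihood will be used "to calculate means and standard errors that will be used in the formation of an ES". It does not say whether T1 enters as a covariate, as an outcome with a separate mean in each arm, or as an outcome with one common mean. The analysis is ITT: "all patients who are complete a baseline assessment and are randomized will be included in our analysis". The observed ES is then compared with a one-sided 80% limit built around ES = 0, which the section offers as "reasonable assurance of making the correct decision to move on to a larger trial".

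Elsewhere the T1 score is prominent. Phase 2 Inclusion Criteria require a GSI T-score above 53. Phase 2 Measures and Materials says this same score gauges eligibility "and will serve as the primary outcome measure". Randomization uses "blocks of size 4 within low and high levels of the baseline psychological distress as measured by the BSI-18", split at 63, and adds that "we will also equalize the treatment groups according to gender". Phase 2 Plan to Address Missing Data uses correlated variables, but only to impute missing values. Phase 2 Sample Size Justification sets N = 32 so that the limit excludes 0.3 SD, with 38 to be randomised. Phase 2 Data Attrition plans for up to 20% loss.

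**The concern.** The design balances the arms on T1 distress, but the stated analysis neither adjusts for T1 nor accounts for the stratification. This has three consequences.

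- The T2 difference carries variation that T1 could explain.
- The two-sample standard error ignores the balance that stratification has already produced. It is therefore too large, and the 80% limit is crossed less than 20% of the time under no effect.
- The MLM wording fits models that give different estimates from the same data, so the primary ES is open to choice.

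Estimating this ES is the first of the three Phase 2 goals, in a trial of at most 38 patients that is meant to inform a larger one.

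**Working it through.** **1. The plan's own figure.** With SD = 1 and no covariate, the half-width is z(0.80) × √(2/n per arm). Setting it to 0.3 gives n = 2 × (0.8416/0.3)² = 15.74, so 16 per arm and N = 32. At 16 per arm the half-width is 0.8416 × √(2/16) = 0.2976. The stated N reproduces only with no baseline term, so the sizing is unadjusted too.

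**2. What the MLM returns.** Let dy be the T2 arm difference in patients with T2 data, dx(obs) the T1 difference in those patients, dx(all) the T1 difference in everyone randomised, and b the common slope.
- Free arm means at each time: dy − b × [dx(obs) − dx(all)]. With complete data the bracket is zero, leaving the raw difference dy.
- T1 means constrained equal, or T1 as covariate: dy − b × dx(obs).

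In one simulated data set with 8 of 38 T2 values missing, the constrained MLM and ANCOVA both gave −0.3129, the free-means MLM −0.2230, and the completers' raw difference −0.1155.

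**3. Size with complete data.** The assumptions, none given in the documents, are:
- r among eligible patients of 0.3, 0.5 or 0.7;
- eligible T1 drawn as integer T-scores 54-81 from a normal with mean 63 and SD 8 (means 58 and 66 also tried).

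The strata, blocks of 4, 1:1 allocation and n = 38 follow the plan. There were 60,000 trials per setting, and each estimator was compared with its own one-sided 80% t limit. Exceedance means crossing that limit in favour of E-PST.

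| T1 mean 63 | r = 0.3 | r = 0.5 | r = 0.7 |
|---|---|---|---|
| True SE, raw difference | 0.315 | 0.298 | 0.272 |
| Mean two-sample SE | 0.323 | 0.323 | 0.324 |
| True SE, T1-adjusted | 0.310 | 0.283 | 0.234 |
| Null exceedance, raw (nominal 20%) | about 19% | 18% | 16% |
| Exceedance at ES 0.3, raw | 52.8% | 53.2% | 53.4% |
| Same, stratum term only | 53.9% | 56.2% | 60.2% |
| Same, T1-adjusted | 54.5% | 58.4% | 67.1% |

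Adjusted null exceedance is about 20% throughout. Over T1 means 58-66 the true SE falls by 1-2%, 5-6% and 13-16%.

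A hand check at r = 0.5, by normal approximation:
- Raw, null: 0.8416 × 0.323/0.298 = 0.912, and the upper tail is 18%.
- Raw, ES 0.3: (0.3 − 0.8416 × 0.323)/0.298 = 0.095, giving 54%.
- Adjusted, ES 0.3: (0.3 − 0.8416 × 0.283)/0.283 = 0.218, giving 59%.

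The textbook factor √(1 − r²) would promise SE cuts of 5%, 13% and 29%. That overstates the true gain, because stratification already captures part of it. The stratum-only row shows how much of the rise is calibration: at r = 0.5, (56.2 − 53.2)/(58.4 − 53.2) = 58%; at r = 0.7, (60.2 − 53.4)/(67.1 − 53.4) = 50%.

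**4. With 20% random loss (38 to 30).** The comparator is the least favourable reading of the MLM: free arm means, with df-corrected variance.

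| T1 mean 63 | r = 0.3 | r = 0.5 | r = 0.7 |
|---|---|---|---|
| True SE, free-means MLM | 0.355 | 0.335 | 0.300 |
| True SE, T1-adjusted | 0.352 | 0.321 | 0.265 |
| Exceedance at ES 0.3, free-means MLM | 47.9% | 49.0% | 50.6% |
| Exceedance at ES 0.3, T1-adjusted | 49.6% | 53.3% | 61.5% |

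Null exceedance is 19%, 18% and 16% for the free-means MLM, against 20% when adjusted.

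**5. Where the gain disappears.** The entry cut may lower r. With T1 mean 63 and SD 8, an unrestricted r of 0.3, 0.5 or 0.7 becomes 0.24, 0.41 or 0.61 among eligible patients. The complete-data SE gain is then 0.6%, 3% and 9%, and exceedance at ES 0.3 is 54%, 56% and 62-63% against 53-54%. For unstratified allocation, break-even is r = √(1/(N − 3)), which is 0.17 at N = 38 and 0.19 at N = 30. A working figure is therefore about 0.2. At r = 0 the covariate costs about 0.6% of the SE with complete data.

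**The case against.** The strongest reply is that silence is not exclusion. The means come from an MLM, and if its authors intend a common T1 mean or a T1 covariate, the plan already contains the fix and the gain is zero. That stands as a limit on the size. It does not remove the point: the only formula written down omits T1, and the free-means model, which fits the text equally well, returns the raw difference when data are complete.

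Second, the gain is small unless r is high, r is unknown, the miscalibration is conservative, and no formal go/no-go rule hangs on the limit. All of this is true. It makes the change an inexpensive improvement and not the repair of an invalid analysis.

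Third, the attrition comparison depends on the variance method. With uncorrected ML variance and a z limit (the plan names no df method), null exceedance for the free-means MLM is 20.8%, 19.1% and 17.3%. At ES 0.3 its exceedance is 51%, 51% and 53%, against 50%, 53% and 61% for the adjusted contrast. At r of 0.3 and 0.5 most of the calibration shortfall then goes, partly because uncorrected ML understates the SE. The gain at 0.7 remains.

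Fourth, adjusted and unadjusted results can fall on different sides of their limits: in 6%, 12% and 20% of complete-data trials at ES 0.3. The SAP must therefore say which one governs. Two simplifications also remain: the T-score ceiling of 81 is assumed, and T3 is left out of the simulation.

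**Conclusion.** The concern holds as a point of efficiency and calibration, not of bias; the unadjusted ES is valid. The benefit is negligible at r = 0.3, modest at 0.5 and clear only at 0.7, and about half or slightly more of the rise in exceedance at ES 0.3 comes from calibration. These sizes rest on the assumed correlations and T1 distribution, a linear T1-T2 relation, loss at random, and a comparator that is either the raw difference or the free-means MLM. Since adjustment costs almost nothing even if r proves low, it should be specified. Confidence is medium because r is not given.

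**What to change.** In Phase 2 Data Analysis, a) Quantitative Data Analysis:

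- State that the primary T2 contrast comes from the MLM with T1 arm means constrained equal, or with the continuous T1 GSI T-score as a covariate. When T1 is complete and only T2 is missing, both give the same contrast. The constrained form keeps patients without T2 in the likelihood, in line with the ITT statement.
- Divide that contrast by the observed, unadjusted pooled T2 SD, so that the ES stays on the 0.3 SD scale of the sample size section.
- Take the one-sided 80% null limit as the t quantile times the model SE (REML or df-corrected), divided by that SD. This replaces the two-group non-central t form as the governing limit.
- Report the unadjusted ES with its non-central t limit beside it, as supportive.
- Use the same adjusted contrast in every imputed data set, so that the MI-versus-MLM comparison reflects missing data only.
- Leave a gender term optional. In simulation (10% female assumed, non-prognostic, arms not equalised) it cost 1.3-2.0% of the SE, enough to cancel the gain at r = 0.3.

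The cost is SAP wording and one degree of freedom. No new data are needed, and the N of 32 and the 0.3 target need not change.

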5. Quantitative data will be summarized using descriptive statistics and graphic displays, with a post-test ES calculated to describe the standardized difference between treatment conditions. Qualitative data will be summarized using a rapid analysis process. Because primary aims of this pilot study involve evaluation of feasibility, attendance at fewer than the intended number of treatment sessions, or participant noncompliance with assessment regimens will not be recorded as protocol deviations. Further, flexibility in scheduling and the timing of participant contact will be offered to evaluate the feasibility of the recruitment and retention plans for our future trial. Ultimately, data gathered in this study will help us to determine the optimal scope, study logistics, and recruitment and retention timelines for our future work.

Phase 2 Participants, Recruitment, and Enrollment.

Potential candidates will primarily be identified using EMR data (i.e., CPRS, Corporate Data Warehouse/VA Informatics and Computing Infrastructure [VINCI]), including patient demographics, coded encounters, and clinic stop codes. Based on prior CIH work, a conservative estimate of a 30% response rate has been assumed for this study. Thus, up to 127 primary care patients will be solicited in order to achieve a maximum randomization of 38 Veterans ($n = 19$ per arm). While we ultimately seek to gather treatment data from 32 Veterans ($n = 16$ per arm), we have adjusted our enrollment projection upward to improve the precision of our confidence interval (CI) estimates. To ensure an adequate mix of participants, we seek to oversample females

[figure not shown]

Figure 2. Pilot RCT Study Flow

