
missing values and satisfying the MAR assumption. We plan to conduct a sensitivity analysis to determine the effect of the missingness by comparing MI to MLE estimation via MLM.

Evaluation of feasibility will focus primarily on descriptive statistics. For instance, means and standard deviations will be calculated for time estimates for each primary and secondary measure and homework assignment. The study team will also record and review frequencies of completed vs. incomplete measures, and any relevant participant comments that pertain to lack of clarity or undue burden of measures. Recruitment over time will be displayed by plotting the cumulative number of patients enrolled into this study and compared to the anticipated rate of recruitment. Any intervention elements with relatively low fidelity will subsequently inform the future training curriculum that will be designed for EPST therapists in our full-scale RCT.

Qualitative feedback on experiences with E-PST (i.e., acceptability treatment satisfaction) and reasons for completion/ dropout will be analyzed via rapid qualitative analysis (Beebe, 2001). Rapid qualitative analysis will facilitate our ability to quickly incorporate patient feedback in planning our future RCT.

Phase 2 Sample Size Justification

a) *Quantitative Methods:* Using previously published ES data on the effect of PST in mTBI10 and the method described by Cocks and Torgerson (2013) we calculated the sample size to adequately employ an 80% one-sided CI to estimate the upper limit of the ES under the null hypothesis of no difference (ES=0) between conditions. The one-sided CI was calculated so that 32 patients allow for the upper limit of an 80% CI to exclude 0.3, or a difference of 0.3 standard deviations, between conditions. While 32 total participants are required to meet these parameters of CI estimation, we will seek to randomize a total of 38 Veterans to increase the precision of our estimate while accounting for the possibility of missed visits (see data attrition section below).

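### The planned effect size has no small-sample correction and its model is fitted by ML rather than REML: a minor, nearly free improvement

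*Combined protocol and SAP*

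**What the plan says.** All of the analysis text is in the combined protocol and SAP, Phase 2 Data Analysis, part (a).

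- The ES is obtained by "dividing the difference in the mean BSI-18 score between conditions at post-treatment by the pooled standard deviation". No small-sample correction is mentioned.
- Further on, the plan states: "A multi-level model (MLM) will be developed using MLE to calculate means and standard errors that will be used in the formation of an ES". REML is not mentioned. No sentence says which SD the pooled SD is: the observed one at T2, a variance component of the model, or something derived from its standard errors.
- The stated goal is to "calculate a preliminary ES estimate that is representative of the true population", and the ES is meant to help in developing a larger trial.
- An 80% one-sided limit, set under no difference between arms, is to be "compared to the observed ES by using the non-central *t*-distribution method".
- The same section plans descriptive SDs by time point and condition, and a sensitivity comparison of multiple imputation (MI) with the ML-fitted model.
- Phase 2 Sample Size Justification says that "32 patients allow for the upper limit of an 80% CI to exclude 0.3, or a difference of 0.3 standard deviations". The target is 38 randomised, 19 per arm, with treatment data sought from 32, 16 per arm.

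**The concern.** A standardised difference with a pooled SD overestimates the population value in small samples, because the reciprocal of a sample SD is biased upward. ML estimation divides the variance by the number of patients rather than by the residual degrees of freedom, so model standard errors come out slightly short. Both faults have standard remedies that cost nothing, Hedges g and REML, and the plan adopts neither although it asks for a representative ES.

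What is at stake is modest. Required sample size varies with 1/ES², so a small relative error in the ES roughly doubles in any later trial sized directly on it. Leaving the divisor unnamed adds a choice that could move the result further than either bias.

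**Working it through.** **Inputs.** 16 and 19 per arm (Phase 2 Participants, Recruitment, and Enrollment), so df = 2n − 2 = 30 and 36. One-sided 80% level and 0.3 SD (Phase 2 Sample Size Justification). Attrition of 6% over 12 weeks and 20% over 6 months, the latter taken as the upper limit (Phase 2 Data Attrition).

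**The plan's own figure.** N = 4 × (0.8416/0.3)² = 31.5, hence 32. At 16 per arm the upper limit is 0.8416 × √(2/16) = 0.298, below 0.3. The stated 32 is reproduced. (With central t on 30 df the limit is 0.302, which would need 17 per arm. That is a separate and trivial matter.)

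**Bias of uncorrected d.** E[d] = ES/J, with J = Γ(df/2) / [√(df/2) × Γ((df−1)/2)], close to 1 − 3/(4 df − 1).

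- df 36: J = 0.979, 1/J = 1.021. A true 0.30 reads 0.306.
- df 30: J = 0.975, 1/J = 1.026. A true 0.30 reads 0.308.
- Shortfall in a later trial sized on it: 1 − J² = 4.2% (df 36) to 5.0% (df 30). For example, assuming two-sided 0.05 and 80% power, 166 per arm instead of 175 at a true ES of 0.30.

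**ML rather than REML.** In a simple two-group fit, the ratio of ML to unbiased-variance standard error is √(df/(df+2)).

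- df 36: √(36/38) = 0.973, or 2.7% too small.
- df 30: √(30/32) = 0.968, or 3.2% too small.

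**Conditional case: ML variance as divisor.** Total inflation is the product of the two factors.

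- df 36: 1.0215 × 1.0274 = 1.049.
- df 30: 1.0259 × 1.0328 = 1.060. A true 0.30 would read 0.318.
- At 15 per arm (38 less about 20%), the total is 6.4%.

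**Against sampling error.** The standard error of d near zero is √(2/16) = 0.354 at 16 per arm. The largest excess at ES 0.30 for that size is 0.018, and 0.018/0.354 is about 5% of one standard error.

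**Effect on the decision.** Chance that the observed ES exceeds 0.3 at 16 per arm, taking d/√(2/n) as noncentral t:

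| True ES | d, pooled SD | d, ML SD | Hedges g |
|---|---|---|---|
| 0 | 0.201 | 0.209 | 0.196 |
| 0.3 | 0.503 | 0.513 | 0.494 |
| 0.5 | 0.715 | 0.725 | 0.708 |

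Shifts are about one percentage point.

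**Why the divisor should be named.** Two readings that the text leaves open would move the ES in opposite directions.

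- Baseline-adjusted residual SD: the ES rises by 1/√(1 − r²), which is 5%, 15% or 40% at an assumed r of 0.3, 0.5 or 0.7. The documents give no correlation.
- SD backed out as SE × √19 with some T2 scores missing: at 20% missing, √(19/15.2) = 1.118, so the ES is about 11% too low. At 6% missing, √(19/17.86) = 1.031, so it is about 3% too low. Both take no information from T1. With an assumed T1–T2 correlation of 0.5 and 20% missing, the factor is √(1 + 0.25 × 0.75) = 1.09, so the ES is about 8% too low.

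**The case against.** A reader might infer that the plan divides by an ML variance, that it mixes model standard errors with a pooled SD, and that it thereby misstates the single result the pilot exists to produce. The documents do not support this:

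- A pooled SD conventionally carries an n₁ + n₂ − 2 divisor, and observed SDs by arm and time point are planned anyway. Nothing says that an ML variance component is the divisor, or that an SD is recovered from a standard error. The model standard errors may serve only for the interval.
- Phase 2 Data Analysis lists three goals. The ES is one, and the other two concern feasibility.
- Adding up only the features that inflate the ES gives a one-sided picture, since an SD backed out of a standard error would deflate it.
- No section says that the later trial will be sized on the raw point estimate. With a standard error near 0.35, a difference of a few percent in that trial's size is well inside the noise.

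There is also a sound argument against putting Hedges g everywhere. The bias is multiplicative and vanishes at ES = 0, where the limit is set, and uncorrected d is the natural input to a t-based comparison. At 30 df the limit is 0.302 and d exceeds it 20% of the time under the null. Multiplying the ES by J without rescaling the limit lowers that to 19.4%.

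All of this stands, and it sets the size and shape of the recommendation. It does not remove the two facts in the text: no correction is named, and ML is the named estimator.

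**Conclusion.** A minor improvement at almost no cost. As written, the ES is 2.1% (36 df) to 2.6% (30 df) too large on average, and ML standard errors are about 3% too small. The latter figure assumes a simple two-group fit, because the plan does not give the model's fixed effects. The 4 to 5% shortfall in a later trial's size holds only if the observed ES is used there unchanged. Inflation of 4.9 to 6.0% depends on an ML divisor that the plan does not state. None of this is material beside sampling error, none of it alters the justification for 32 patients, and it would move the chance of passing 0.3 by about one percentage point. The unnamed divisor is missing detail rather than a demonstrated error, but it is worth settling in the same edit.

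**What to change.** In Phase 2 Data Analysis, part (a):

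1. Fit the multilevel model by REML.
2. Define the divisor as the unadjusted T2 between-person SD pooled over arms. Rule out an SD backed out of a standard error and a baseline-adjusted residual SD. Use the same divisor in the model-based and MI analyses, so that their comparison reflects the handling of missing data only.
3. Report Hedges g = d × J, with J = 1 − 3/(4 df − 1), beside d, as the figure for planning the larger trial.
4. Keep the noncentral-t interval and the comparison with the 80% limit on uncorrected d, so that the calibration of that comparison is undisturbed.

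The cost is two or three sentences and one software option. Sample size and trial conduct do not change. The only downside is a slightly less favourable reported ES.
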